At randomization, subjects will be provided with a drug kit containing either open-label Edoxaban or Warfarin for 30 days at a randomization visit. Patients randomized to Warfarin will take Warfarin on the day of procedure and patients randomized to Edoxaban will receive no drug on the day of the procedure.

Routine clinical care will be implemented with patients being scheduled for discharge within 24 hours of admission to maintain ambulatory procedural status. Patients requiring longer lengths of stay will have documentation of conditions warranting such care.

The routine standard of care (SOC) is instituted after the procedure, with a pre-discharge visit (4 to 24 hours after procedure), wound care visit (usually 1 to 2 weeks after the procedure) and standard device clinical follow-up procedures. These can include one month, three month or six month visits or remote monitoring as clinically employed in the study.

In the event of an acute procedural bleed, blood products or vitamin K may be administered. In this case, the patient will be counted as having met the primary endpoint. The primary outcome of major bleed will be assessed at the 30-day visit. The medical monitor will confirm that the primary endpoint has been assessed.

After the 30-day assessment, patients will continue to take the randomized anticoagulant unless it becomes medically necessary to change it. The MACE components will be collected at the time of the 6-month in-clinic visit.

There will be a telephone follow-up at 3 months after the CIED procedure for MACE and hospitalizations and vital status. There will be a face to face visit at 6 months which will result in study follow up completion and final patient assessment for safety endpoints, hospitalizations and vital status.

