4.2 Justification of key elements of study design

4.2.1 Primary Endpoint

Peri-procedural bleeding and major local bleeding is of clinical concern for patients who require anticoagulation. Though catastrophic bleeding is rare, bleeding requiring clinical intervention is more frequent and can be studied in a modestly sized trial. Unlike strict use of change in hemoglobin, the need for intervention with vitamin K or blood products is recognizable to patients. Reduction in the need to administer an intervention for a procedural bleed should also result in lower health care resource utilization and costs.

Major local or systemic bleeding is defined as one of the following events:

- Significant hematoma requiring further surgery, resulting in prolongation of hospitalization, or requiring interruption of oral anticoagulation therapy
- Blood transfusion (permitted if hemoglobin is below 8 gm%, or 9 gm% in patients with active myocardial ischemia e.g. acute coronary syndrome)
- Surgical or interventional procedure to control bleeding that is symptomatic (shock, severe hypotension (90 mm hg systolic) or angina or myocardial infarction, which is not amenable to conservative measures (pressure dressing, ice packs) or volume expansion with intravenous fluids)
- Use of reversal agent injection to control bleeding leading to clinically manifest shock (e.g. hypotension requiring pressors, oliguria etc.) or death, severe and symptomatic hypotension (90 mm hg systolic or lower) or angina or hemoglobin decline to below 8 gm% not amenable to conservative measures (pressure dressing, ice packs or volume expansion with intravenous fluids)
- Hemorrhage leading to stroke or eventual fatality

(INR- guidelines for vitamin K injection or blood products will be established- see guideline below).

(aPTT or anti- factor Xa assay may or may not be available for Edoxaban to guide reversal – clinical and Hemoglobin guidelines as established above will be employed to guide use of reversal with blood products or transfusion).

Recommendations for Managing Elevated INRs or Bleeding in Patients Receiving VKAs

Condition	Suggested Intervention
INR less than 4.5 but above	Hold or reduce Warfarin dose. Resume Warfarin when INR is therapeutic.

therapeutic	

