INR 4.5 to 10 with no evidence of bleeding	
Hold Warfarin. Resume Warfarin when INR is therapeutic.
 
Vitamin K not routinely recommended if no evidence of bleeding.
 
Vitamin K can be used if urgent surgery needed (less than 5 mg, with additional 1 to 2 mg in 24 hrs. if needed) or bleeding risk is high (1 to 2.5 mg).

INR greater than 10 with no evidence of bleeding	
Hold Warfarin therapy and administer vitamin K 2.5 mg to 5 mg orally.
 
Monitor INR.
 
Resume Warfarin at lower dose when INR therapeutic.

Serious bleeding at any elevation of INR or Life-threatening bleeding	
Consult Hematology.
 
Hold Warfarin.
 
Administer intravenous vitamin K 5 mg to 10 mg by slow infusion or administer blood products as appropriate.

*In patients with mild to moderately elevated INRs without major bleeding, give vitamin K or blood products as appropriate. Adapted from ACCP Evidence-Based Clinical Practice Guideline *Chest* 2012; 141(Suppl 2): e154S-88s.

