4.2.3 Timing of primary endpoint evaluation

Other studies in cardiovascular medicine such as those for interventions during acute myocardial infarction or chronic ischemic heart disease consider bleeding events through 30-days post-procedure, and so it is a commonly used clinical timeframe. Because this trial is examining a surgical intervention, there is potential for bleeds and other acute complications. If this happens, the open label design allows investigators to make appropriate treatment decisions as quickly as possible. As always, open-label designs have an increased risk of bias. To combat this risk, we have defined a primary endpoint with minimal patientivity (see section 4.2.1). We will also have a blinded adjudication committee review each potential primary endpoint event to confirm that the study definition has been met.

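### Sections 4.1 and 4.2.1 give different rules for when vitamin K or a non-red-cell reversal product makes a procedural bleed a primary event, and nothing says which governs

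*Combined protocol and SAP*

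**What the plan says.** **Section 4.1 (Overview).** "In the event of an acute procedural bleed, blood products or vitamin K may be administered". The next sentence reads "In this case, the patient will be counted as having met the primary endpoint". It sets no condition on severity, hemoglobin or route of administration.

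**Section 4.2.1 (Primary Endpoint).** Major bleeding is any one of five listed events. Three matter here:

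- The reversal item begins "Use of reversal agent injection to control bleeding leading to clinically manifest shock". It goes on to death, severe symptomatic hypotension, angina, or a hemoglobin fall below 8 gm% that conservative measures cannot manage.
- The transfusion item stands alone: "Blood transfusion (permitted if hemoglobin is below 8 gm"%, or 9 gm% with active ischemia. It needs no shock or angina.
- The hematoma item counts a significant hematoma that needs surgery, prolongs the stay or requires interruption of oral anticoagulation.

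The rationale in the same section says that "the need for intervention with vitamin K or blood products is recognizable to patients", which is closer to the 4.1 rule.

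**Treatment guidance in 4.2.1.** For Edoxaban, "clinical and Hemoglobin guidelines as established above will be employed to guide use of reversal with blood products or transfusion". The INR table is for patients on vitamin K antagonists. Its footnote says "In patients with mild to moderately elevated INRs without major bleeding, give vitamin K or blood products as appropriate" and sets no hemoglobin limit.

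**Section 4.2.3.** After pointing to 4.2.1 for the endpoint, it says "We will also have a blinded adjudication committee review each potential primary endpoint event to confirm that the study definition has been met".

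The synopsis refers only to major bleeding as the protocol defines it, and both sections are part of the protocol.

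**The concern.** Take a patient with a minor procedural bleed who receives vitamin K, stays hemodynamically stable, keeps a hemoglobin above 8 gm%, has no prolonged stay and does not interrupt anticoagulation. Section 4.1 counts this patient as a primary event. No item in 4.2.1 does. A site that follows one section and a committee that follows the other would classify the same bleed differently.

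The trial is open label, and under the 4.1 rule the treating physician's decision to give a product creates the event. Vitamin K reverses Warfarin, and the permissive footnote concerns Warfarin patients, whereas reversal or transfusion on Edoxaban is tied to clinical and hemoglobin limits. Extra events under 4.1 could therefore fall mainly on Warfarin and make non-inferiority of Edoxaban easier to declare. If they fell equally on both arms, they would add noise and cost power. Few events are expected, so single classifications matter.

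**Working it through.** **1. The two rules side by side, by treatment given for an acute procedural bleed**

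| Treatment and setting | 4.1 | 4.2.1 |
|---|---|---|
| Vitamin K or non-red-cell reversal product, with shock, death, severe symptomatic hypotension, angina or Hb below 8 gm% | event | event if given by injection (reversal item) |
| Same products, none of these, but a significant hematoma with interrupted anticoagulation or longer stay | event | event (hematoma item) |
| Same products, none of the above | event | **no event** |
| Red cells below the hemoglobin limit | event | event (transfusion item) |
| Red cells above the limit | event | unclear: the limit may be a condition for scoring or only treatment guidance |

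The firm conflict is the third row. The fifth is an ambiguity within 4.2.1.

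**2. The plan's own power figure**

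Inputs (sections 10 and 10.2): Warfarin 3.51%, Edoxaban 0.5%, margin 1.5 points, one-sided 0.025, 300 patients, stated power about 80%. Allocation is 1:1 (section 4.1), so 150 per arm.

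- SE = √(0.0351×0.9649/150 + 0.005×0.995/150) = 0.0161
- (0.0351 − 0.005 + 0.015)/SE = 0.0451/0.0161 = 2.80
- Power = Φ(2.80 − 1.96) = 0.800

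The stated figure reproduces. An exact unconditional test ordered by the Farrington-Manning score (critical score 1.996, size held to 2.5% over all Warfarin rates, interim look ignored) gives 79.6%. The figures below use this test.

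**3. What an excess would do**

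Let x be the points that the 4.1 rule adds to an arm's event rate. The documents give no value, so x is assumed. At 150 per arm, x = 0.67 points is 0.0067 × 150 = 1 patient, against 0.0351 × 150 = 5.3 expected Warfarin events.

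*Chance of declaring non-inferiority when the true 4.2.1 rates sit at the margin (Edoxaban 5.01%, Warfarin 3.51%):*

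| x on Warfarin | Warfarin only | Half as much on Edoxaban | Equal in both arms |
|---|---|---|---|
| 0 | 2.0% | 2.0% | 2.0% |
| 0.33 | 2.8% | 2.4% | about 2.0% |
| 0.67 | 3.7% | 2.75% | about 2.0% |
| 1.33 | 6.3% | 3.6% | 2.1% |

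*Power at the planned rates when both arms gain x:* 79.6% at x = 0, then 71.8%, 65.1% and 54.4% at 0.33, 0.67 and 1.33 points.

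**4. Why single events matter**

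At 150 per arm, 0, 1 or 2 Edoxaban events pass the test with at least 2, 4 or 6 Warfarin events. At the planned rates, one added Warfarin event turns failure into success in 8.4% of trials.

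**The case against.** The strongest reply is that the protocol already points to one rule. Section 4.1 is an overview, 4.2.1 carries the definition, and 4.2.3 refers to 4.2.1 and sends every potential event to a blinded committee. On that reading, 4.1 is a loose summary and nothing is lost. This largely stands: 4.2.1 is the likelier rule. But the 4.1 sentence is categorical, no text subordinates it, and the 4.2.1 rationale itself leans on the need for vitamin K or blood products. Section 7 also names the order for these products as documentation of intervention, without a severity limit. The committee can apply one rule only if it is given one.

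Three stronger readings are tempting, and the documents do not support them:

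- *Every use of blood products is in conflict.* It is not. Transfusion has its own item in 4.2.1. Nor does all vitamin K fall outside: the INR-table row for serious bleeding also holds Warfarin, so some of these patients could score through the hematoma item.
- *The trial is biased toward Edoxaban.* The direction is inferred from which drug vitamin K reverses. The documents give no frequency of such treatment in either arm. The larger figures above also need the whole excess on Warfarin, survival through blinded adjudication, and a true Edoxaban rate ten times the planned one. They measure error only if 4.2.1 is the intended endpoint; if 4.1 is, the added events are genuine.
- *The INR guidance should be tightened.* The footnote concerns patients without major bleeding. Adding hemoglobin limits there would change care to suit an endpoint. It would also contradict the footnote's own population, because a patient transfused below 8 gm% meets the major-bleeding definition.

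**Conclusion.** The concern holds in a narrow form. The protocol gives two incompatible rules for vitamin K and non-red-cell reversal products used for a bleed that meets no other 4.2.1 item, and it does not rank them. A lesser ambiguity remains over whether the transfusion hemoglobin limit is a condition for scoring.

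The size is unknown, and it is zero if the committee applies 4.2.1 strictly. With one extra Warfarin patient in 150, the chance of declaring non-inferiority at the margin would be 3.7% instead of 2.0%. With one extra patient in each arm, power would be 65.1% instead of 79.6%. Both illustrations rest on an assumed excess that survives adjudication, on 4.2.1 being the intended endpoint, on fixed arms of 150 and on the planned rates. This is a primary-endpoint inconsistency that should be corrected; it is not evidence of a biased result.

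**What to change.** 1. In section 4.1, replace "In this case, the patient will be counted as having met the primary endpoint" with: *The patient counts as a primary event only if the bleed meets the 4.2.1 definition, as confirmed by the blinded adjudication committee.*
2. In section 4.2.1, add: *Vitamin K or blood products given for an INR value, or for bleeding that does not meet this definition, do not score as a primary event.*
3. In the transfusion item, state whether a transfusion above the hemoglobin limit scores. This is a clinical decision.

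If the sponsor meant an intervention-based endpoint, the alternative to edits 1 and 2 is to drop the severity conditions from the reversal item so that 4.2.1 matches 4.1. Either way, one rule must apply to both arms. Leave the INR table and its footnote as they are.

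The cost is a few sentences of protocol text, matching wording for the adjudication committee and a memo to sites. No new data or patients are needed. The possible downside of making 4.2.1 govern is slightly fewer counted Warfarin events. If the Warfarin rate fell 0.33 points below plan (3.51 − 0.33 = 3.18%), power at 150 per arm would be 74.9% instead of 79.6%. If the removed events would have fallen equally on both arms, the change protects the planned power.

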4.2 Justification of key elements of study design

4.2.1 Primary Endpoint

Peri-procedural bleeding and major local bleeding is of clinical concern for patients who require anticoagulation. Though catastrophic bleeding is rare, bleeding requiring clinical intervention is more frequent and can be studied in a modestly sized trial. Unlike strict use of change in hemoglobin, the need for intervention with vitamin K or blood products is recognizable to patients. Reduction in the need to administer an intervention for a procedural bleed should also result in lower health care resource utilization and costs.

Major local or systemic bleeding is defined as one of the following events:

- Significant hematoma requiring further surgery, resulting in prolongation of hospitalization, or requiring interruption of oral anticoagulation therapy
- Blood transfusion (permitted if hemoglobin is below 8 gm%, or 9 gm% in patients with active myocardial ischemia e.g. acute coronary syndrome)
- Surgical or interventional procedure to control bleeding that is symptomatic (shock, severe hypotension (90 mm hg systolic) or angina or myocardial infarction, which is not amenable to conservative measures (pressure dressing, ice packs) or volume expansion with intravenous fluids)
- Use of reversal agent injection to control bleeding leading to clinically manifest shock (e.g. hypotension requiring pressors, oliguria etc.) or death, severe and symptomatic hypotension (90 mm hg systolic or lower) or angina or hemoglobin decline to below 8 gm% not amenable to conservative measures (pressure dressing, ice packs or volume expansion with intravenous fluids)
- Hemorrhage leading to stroke or eventual fatality

(INR- guidelines for vitamin K injection or blood products will be established- see guideline below).

(aPTT or anti- factor Xa assay may or may not be available for Edoxaban to guide reversal – clinical and Hemoglobin guidelines as established above will be employed to guide use of reversal with blood products or transfusion).

Recommendations for Managing Elevated INRs or Bleeding in Patients Receiving VKAs

Condition	Suggested Intervention
INR less than 4.5 but above	Hold or reduce Warfarin dose. Resume Warfarin when INR is therapeutic.

therapeutic	
INR 4.5 to 10 with no evidence of bleeding	
Hold Warfarin. Resume Warfarin when INR is therapeutic.
 
Vitamin K not routinely recommended if no evidence of bleeding.
 
Vitamin K can be used if urgent surgery needed (less than 5 mg, with additional 1 to 2 mg in 24 hrs. if needed) or bleeding risk is high (1 to 2.5 mg).

INR greater than 10 with no evidence of bleeding	
Hold Warfarin therapy and administer vitamin K 2.5 mg to 5 mg orally.
 
Monitor INR.
 
Resume Warfarin at lower dose when INR therapeutic.

Serious bleeding at any elevation of INR or Life-threatening bleeding	
Consult Hematology.
 
Hold Warfarin.
 
Administer intravenous vitamin K 5 mg to 10 mg by slow infusion or administer blood products as appropriate.

*In patients with mild to moderately elevated INRs without major bleeding, give vitamin K or blood products as appropriate. Adapted from ACCP Evidence-Based Clinical Practice Guideline *Chest* 2012; 141(Suppl 2): e154S-88s.

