In the BRUISE control study AF patients with PM or ICD devices were studied using two different regimens for peri-procedural anticoagulation. Birnie et al reported “clinically significant” device pocket hematomas in 3.5% of on Warfarin and in 16% of patients on heparin bridging therapy.⁽³⁾ In another multi-center study, 9.8% of patients on heparin or Warfarin had significant pocket hematomas after pacemaker implantation.⁽⁴⁾ This is in contrast to the general CIED population, in whom this complication was observed only in 0.2% of implanted individuals in a nationwide experience from Denmark.⁽⁵⁾ Kutinsky et al reported even higher rates of hematoma formation in the presence of clopidogrel and aspirin with continued Warfarin therapy ranging from 9.5 to 24%.⁽⁶⁾ Bleeding complications predispose patients to interruption of OAC therapy, use of reversal agents, infection, and re-operation and prolong hospital stays. Bridging therapy may be associated with increased embolic events due to varying anticoagulation status.⁽³⁾

In contrast, in the MOST study performed in patients with only sick sinus syndrome at entry, bleeding complications with pacemaker implantation were <0.4%.⁽⁷⁾ Dewland et al reported major complication rates with ICD implants in the National Cardiovascular Device registry. They noted device related complications of approximately 1% exclusive of major bleeding and hematomas with ICD implants.⁽⁸⁾

2. Purpose and Rationale

The rationale of this study is based on the long half-life of Edoxaban and its potential for reduced bleeding risk in comparison to Warfarin in patients with non-valvular AF. Continuous Warfarin therapy has been advocated to avoid the need for bridging anticoagulation at the time of elective surgical procedures such as CIED insertions or revisions. Bridging can increase bleed rates and prolong hospital stay. However, clinical studies show major bleeding complications in 43.5% of such patients in the perioperative period. (3) It is proposed that Edoxaban 60 mg when administered up to 18 to 24 hours before after the CIED procedure and resumed 12 to 24 hours after the procedure could potentially reduce this bleeding risk without loss of efficacy in stroke prevention.

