3.3 Exploratory Objectives

The exploratory objectives are:

1. To compare rates of hemoglobin reductions of ≥ 2 g/L from pre-procedure to 24-48 hours post procedure in the Edoxaban and Warfarin groups
2. To compare change in hemoglobin from pre-procedure to 24-48 hours post procedure in the Edoxaban and Warfarin groups
3. To compare the rates of other events of interest, including
 - Hemoglobin decrease of 1.5Gm% or greater after 24 to 48 hrs
 - Other cardiac procedures
 - Hematoma requiring no intervention
 - Device Infection
 - Device explanation
 - Major intracranial hemorrhage
 - Vascular events
 - Myocardial Infarction (MI)
 - Cardiovascular Hospitalization
 - Hospitalization after procedure discharge and prior to study conclusion
 - Stroke and death composite

4. Study Design

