6.1.1 Run-in Phase

Warfarin may be taken once per day. The allowable doses are 1- 20 mg per day. Subjects should be reminded of dietary and other interactions relevant to Warfarin.

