6.1.3 Follow-up Open Label Phase

[figure not shown]
Subjects randomized to continuous Warfarin should have an INR in the first month, and continue monthly INRs as per standard practice guideline recommendations. Warfarin dosage should be adjusted according to standard practice to keep patients in the therapeutic range. Subjects randomized to Edoxaban should take it once daily per package dosing instructions (Edoxaban 60 mg daily dose for

creatinine clearance 50 to 95 ml/min and Edoxaban 30 mg for creatinine clearance of 30 to 49 ml/min). Subjects will be followed for an additional five months with a phone follow up at 3 months (± 1 week) and final follow up visit at 6 months (± 1 week). After the final follow up visit or after the subject is terminated from the study, subjects on Edoxaban transitioning to Warfarin should be maintained on Edoxaban until the INR is 2.0 or higher before Edoxaban discontinuation in accordance with drug labeling.

7. Study Visits

This study consists of three parts: a run-in or eligibility phase, an acute phase and a follow-up phase. Figure 2 for shows a diagram of study activities. Table 2 and Appendix A show visits.

Figure 2: Study events

Eligibility will be assessed when subjects have completed 3 weeks of Warfarin dosing. The procedure should be scheduled 5 to 15 days after randomization so that subjects are adequately anticoagulated with Warfarin or Edoxaban. The last dose of Edoxaban will be administered less than 24 hours prior to the procedure. Randomization will be obtained via IVRS once eligibility has been confirmed and the procedure has been scheduled.

On the day of the procedure, Warfarin will be continued and Edoxaban will be interrupted. Edoxaban dosing will resume a minimum of 16 and a maximum of 24 hours following the procedure. During and after the procedure, subjects will be assessed for safety and efficacy endpoints for bleeding and

embolism respectively as well as major adverse cardiovascular events (MACE). Edoxaban subjects will in general be discharged on the same day as the procedure, whereas Warfarin subjects will have their discharge timing determined on an individual basis by the investigator.

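### The criterion that counts a hematoma because anticoagulation was interrupted can apply differently by arm during the planned Edoxaban pause, and the plan does not say whether a delayed restart counts

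*Combined protocol and SAP*

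**What the plan says.** Section 4.2.1 (Primary Endpoint) lists the events that make a major bleed. The first is "Significant hematoma requiring further surgery, resulting in prolongation of hospitalization, or requiring interruption of oral anticoagulation therapy". The three consequences are alternatives, so interruption of anticoagulation is enough without surgery or a longer stay. Section 3.3 places "Hematoma requiring no intervention" among the exploratory events.

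The arms are handled differently around the procedure. Section 7 (Study Visits) states: "On the day of the procedure, Warfarin will be continued and Edoxaban will be interrupted". Section 4.1 says that "patients randomized to Edoxaban will receive no drug on the day of the procedure". Section 7 then gives the restart rule: "Edoxaban dosing will resume a minimum of 16 and a maximum of 24 hours following the procedure". Section 2 gives a different window, with Edoxaban "resumed 12 to 24 hours after the procedure".

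No section defines interruption for a patient who is already off drug by plan, or says whether restarting Edoxaban late because of a hematoma is an interruption. Section 4.2.3 accepts that an open-label design risks bias and relies on an endpoint with little subjectivity and on blinded adjudicators, who check that the study definition is met.

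**The concern.** The trial compares a continuous regimen with an interrupted one, and one route to the primary endpoint is that treatment was interrupted. Suppose two patients have the same pocket hematoma a few hours after the procedure, both are managed only by giving no anticoagulant, and both are back on treatment by 24 hours. If a Warfarin dose fell due in that time and was withheld, the Warfarin patient has a primary event. The Edoxaban patient missed nothing that was scheduled, and the hematoma can be recorded as exploratory.

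Blinded adjudication does not repair this. Applying a definition correctly reproduces any asymmetry that the definition contains.

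The lost Edoxaban events would push towards non-inferiority, and then towards the superiority test that follows it (sections 4.2.4 and 10.4). With about 5 Warfarin events expected and a margin of 1.5 percentage points, a few differently scored hematomas matter.

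**Working it through.** **1. Where the asymmetry lies.** Reading sections 4.1, 4.2.1 and 7 together:

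| Situation | Warfarin | Edoxaban |
|---|---|---|
| Hematoma needing surgery or prolonging the stay; bleed meeting another criterion | counts | counts |
| Early hematoma, drug withheld only, treatment back by the end of the restart window | counts if a dose was due and withheld | can go uncounted |
| Early hematoma that delays the Edoxaban restart past the window | not applicable | not stated |
| Hematoma after Edoxaban has restarted, drug withheld | counts | counts |

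Only the second and third rows are at issue. The second also depends on when Warfarin is taken. Section 6.1.1 says, for the run-in, "Warfarin may be taken once per day", and no clock time is given anywhere. If the procedure-day dose was taken before the procedure, the next one falls near the Edoxaban restart and the exposed window is small. With evening dosing it is wider.

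**2. The plan's own power figure.** Inputs from sections 10 and 10.2: Warfarin 3.51%, Edoxaban 0.5%, margin 1.5%, one-sided 0.025, 300 patients. Allocation is 1:1 (section 4.1), so 150 per arm.

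- Standard error = √[(0.0351 × 0.9649 + 0.005 × 0.995) / 150] = 0.01609
- Distance from the margin = 0.015 + 0.0351 − 0.005 = 0.0451
- 0.0451 / 0.01609 − 1.960 = 0.843, so power = 80.0%

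This matches the stated figure of about 80%. Enumerating all binomial outcomes with a Farrington-Manning score test gives 79.6%. That test is used below. Section 10.3 says only that an exact test will be used, so the score test is a stand-in.

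**3. Effect on false non-inferiority.** Let the true Edoxaban rate sit at the margin: 3.51% + 1.5% = 5.01%. Let f be the share of all Edoxaban primary events that would have qualified only through an early hold and so go uncounted. Warfarin stays at 3.51%. The observed Edoxaban rate is 5.01% × (1 − f).

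| Assumed f | Observed Edoxaban rate | Chance of declaring non-inferiority |
|---|---|---|
| 0% | 5.01% | 2.4% |
| 5% | 4.76% | 3.0% |
| 10% | 4.51% | 3.8% |
| 25% | 3.76% | 7.5% |
| 50% | 2.51% | 21% |

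At f = 1 − 3.51/5.01 = 30%, the observed rates are equal and the whole margin has been absorbed.

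The documents do not give f. Appendix B breaks the external Warfarin bleeds down by procedure type, not by timing or by which criterion was met.

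**4. Sensitivity to one event.** Expected events at 150 per arm are 150 × 0.0351 = 5.3 on Warfarin and 150 × 0.005 = 0.75 on Edoxaban. With 5 Warfarin events, the score statistic is 2.27 with 1 Edoxaban event and 1.84 with 2, against a critical value of 1.96. At that count, a single hematoma scored differently changes the conclusion.

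**The case against.** The strongest reply is that the exposed group is narrow. To be lost, a hematoma must be early, managed only by withholding drug, and settled by the scheduled restart. Surgery, a longer stay, transfusion and the other listed criteria count in both arms, and section 4.1 counts any acute procedural bleed treated with blood products or vitamin K. All of this stands. A reader might infer that any early hematoma scores on Warfarin and not on Edoxaban; the documents do not support that.

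A reader might also infer that an Edoxaban patient cannot meet this criterion during the pause. The text does not go that far. A hematoma that pushes the restart past the window can plainly be read as requiring interruption, and nothing excludes it. That is an ambiguity, not a stated exclusion. Counting late restarts would close part of the gap, but not the part inside the pause.

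Nor is it established that the composite endpoint as a whole favours Edoxaban. Under section 7, Edoxaban patients generally go home the same day, while Warfarin discharge is left to the investigator. An Edoxaban patient kept in for a hematoma could meet the prolonged-stay route more readily than a Warfarin patient with no fixed discharge time. That would act in the opposite direction.

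Finally, f could be close to zero. At 5 or 10% the false-positive rate is 3.0% or 3.8%, a modest excess. This stands too, and is why the table starts at 0%.

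**Conclusion.** The concern holds for the interruption criterion only. As written, that criterion depends on a feature of treatment that differs by arm. For early hematomas managed solely by withholding drug, it can count Warfarin cases and miss matching Edoxaban cases. On this criterion the direction favours Edoxaban; for the whole endpoint the net direction is not known.

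The size cannot be derived from the documents. The range of 2.4% to 21% for false non-inferiority assumes 150 per arm, a true Edoxaban rate at the margin, all Warfarin holds counted, the score test, and an uncounted share between 0 and 50%. It would be wrong to quote the upper figures as the trial's error rate. It would also be wrong to infer an error in the sample size, which reproduces.

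This is a should-fix point and a cheap improvement. The case for acting is that so few events are expected and the wording is easily made neutral.

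**What to change.** - In section 4.2.1 and in the adjudication charter, define the criterion by one clock for both arms: a hematoma because of which oral anticoagulation is withheld beyond the end of the protocol's Edoxaban resumption window. State that a hematoma-driven delay of the Edoxaban restart past that point counts.
- State how once-daily Warfarin doses map to that clock, and record actual dose times in both arms so that the rule can be applied.
- Reconcile the two restart windows (12 to 24 hours in section 2, 16 to 24 hours in section 7). No view is taken here on which is right.
- Report the primary endpoint in two sensitivity analyses: (i) without the interruption criterion, and (ii) counting every hematoma-driven Warfarin hold.
- When interpreting the prolonged-stay route, note that the discharge rules differ by arm.

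The cost is a short change in 4.2.1 and in the charter, dose-time fields on the case report form, and two tables. It should be made before events are adjudicated, because a later redefinition in an open-label trial would look data-driven. The downside is that short Warfarin holds stop counting, so the Warfarin rate may fall below the planned 3.51% by an amount that cannot be computed from the documents.
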